## **9. STUDY PROCEDURES**

After informed consent, participants will be asked to complete screening questions to assess for eligibility criteria. Subjects who are not eligible will be told immediately and the module will end. Subjects who are eligible will be randomized to either Group 1 (Website) or Group 2 (Delayed Treatment Control). Randomization will be completed using manual 50/50 chance randomization. After randomization, subjects will complete the remaining baseline surveys (see details on the assessment battery below).

Once baseline surveys are complete, subjects in Group 1 will receive immediate access to the website. After 6 weeks, all subjects will be re-contacted to complete timepoint 2 surveys. User implementation data will be gathered through the website. To further assess acceptability, satisfaction, and barriers and facilitators of website use, selected participants will complete qualitative interviews over HIPAA-compliant Zoom or telephone. Interviews will be recorded and later transcribed verbatim. Participants will be selected for interviews based on patterns of website usage, personal demographics such as race, ethnicity, job title, and years of experience, and school geographic setting. A total of 5 participants will be interviewed from Group 1 at Timepoint 2.

After completion of Timepoint 2 assessment, Group 2 will receive access to the website (Group 1 will retain access to the website). After another six weeks, all subjects will complete Timepoint 3 assessments. A total of 5 participants will be interviewed from Group 2 at Timepoint 3, selected using the same procedure as for Timepoint 2.

The study coordinator will email participants to the email they provided to inform them they have access to the website and alert them to their login information.

Participants will be prompted to complete surveys upon reaching each timepoint via automated

invitation sent to the email they provided in REDCap. If they do not complete the surveys within three days, they will be sent another email reminder. If they do not complete the surveys within a week after the first reminder, they will be called by the study coordinator.

The project coordinator will track participants in REDCap once enrolled and will facilitate timely completion of research assessments. All participants will be encouraged to complete assessments, regardless of their level of engagement with the FMF Connect Teacher Companion website. Actual user data from the website (whether minimal or extensive) will be important in addressing study aims.

Study Assessment Battery

Measure	Number Items	Baseline	T2	T3
Screening and Demographics Measure: This includes both the screening questions and demographics including information about teaching experience and setting	39	X		
FASD Knowledge survey: This was adapted from FMF Connect trials and assesses knowledge about FASD	28	X	X	X
Perceived Self-Efficacy: The Teacher Self Efficacy Scale (TSES) measures teachers' sense of self-efficacy in teaching and supporting students in the classroom	10	X	X	X
Behavioral Attributions: Attributions are measured by the Reasons for Children's Behavior (RCB) across seven subscales of behavior and willful or ability-based attributions.	30		X	X
Behavioral Strategies: The Behavioral Strategies measure was co-normed with the RCB and assesses opinions about common behavioral strategies in the classroom	36	X	X	X
Time spent on student: These questions assess how much time on average the teacher spends planning for their student with FASD.	3	X	X	X
Study Design Feasibility and Acceptability: The Study Experiences Survey (SES) was developed for this study and assesses participants' experiences with the study procedures	10		X	
Program Satisfaction: The Mobile	32		Group 1	X

Application Rating Scale – User Version (uMARS) assesses functionality, usefulness, and helpfulness of technology and information. It is originally used for apps but has been adapted for a website.				
Qualitative Interview on User Experience: This is a 30-45 semi-structured interview assessment participants' experiences of using the website and participating in the study (see uploaded questioning route)	N/A		Group 1	Group 2
Total number of items at each timepoint		116	149 (Group 1) 117 (Group 2)	139

Qualitative Interview. The semi-structured questioning route will cover the following topics: 1) overall impressions of the FMF Connect Teacher Companion website; 2) experience using the website (both facilitators and barrier of use); and 3) perceived impact on their teaching and classroom experience. Interviews are expected to last about 30-45 minutes.

FMF Connect Teacher Companion website. The FMF Connect Teacher Companion website is designed to offer teachers evidence-based education about FASD and strategies to support students with FASD. It is adapted from the FMF Program and FMF Connect, evidence based interventions to support caregivers of children with FASD. The FMF Program and FMF Connect aim to improve caregivers' efficacy and satisfaction as a parent, efficacy, attributions for their child's behavior, and the parent-child relationship. This study will test if the FMF Connect Teacher Companion website is feasible and acceptable, and measure its preliminary effect on these outcomes in teachers.

Usage data from the website will be collected using Azure Application Insights. Application Insights allows to identify website utilization patterns like, for example, number of active users, number of sessions per user, or specific features that the participants use the most.

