## **2. BACKGROUND AND RATIONALE**

Fetal alcohol spectrum disorders (FASD) affect an estimated 1.1-5% of children in the US (May et al., 2018) and can impact various aspects of neurodevelopment, including executive functioning, behavior, and academic performance. Although the majority of individuals with FASD are not intellectually disabled (Mattson et al., 2011), children with FASD perform lower than nonexposed individuals in academics (Crocker et al., 2015; Glass, 2016; Howell et al., 2006; Jirikowic et al., 2008). Without appropriate support, deficits in executive functioning and self-regulation may lead to difficulty organizing materials, planning, and sustaining attention as well as emotional and behavioral dysregulation. Teachers often lack understanding of FASD, leading to ineffective strategies and frustration. Lack of awareness and insufficient training on FASD in the school system creates significant barriers to services for children with FASD (Dybdahl & Ryan, 2009; Koren et al., 2010; Millar et al., 2017; Ryan & Ferguson, 2006; Ryan et al., 2006). Parents often report struggling to obtain services and supports for their children in schools and describe having to educate teachers and staff about FASD (Petrenko et al., 2014; Petrenko et al., 2020; Ryan & Ferguson, 2006; Ryan et al., 2006).

In-person trainings are limited in reach, while a digital intervention delivered via the internet can provide broader access and flexibility. The Families Moving Forward (FMF) Program is a scientifically-validated behavioral consultation program developed at Seattle Children's Research Institute/University of Washington by [name] and colleagues (Bertrand, 2009; Olson & Montague, 2011; Petrenko et al., 2017). It is usually delivered in person or via telehealth by trained specialists. It is designed for caregivers of

children with FASD and includes an in-person, targeted school consultation in which a specialist works with school staff to educate them on FASD, build a more positive home-school relationship, and discuss ways to better support the student. Educating teachers to increase their knowledge and awareness of FASD is hypothesized to help them to modify their attributions of the student's behavior and use more effective behavioral strategies, leading to improved self-efficacy and student-teacher relationship.

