## 17. DATA ANALYSIS PLAN

Qualitative Interview Data: Data will be analyzed thematically to understand users' experiences with the FMF Connect Teacher Companion website and research trial. Thematic analysis focuses on identifying patterns or themes within the data. Consistent with the approach advocated by Miles, Huberman, and Saldana (2014), research team members will first familiarize themselves with the data, iteratively reviewing each transcript, and independently assigning initial codes (“first-level coding”). The team will then come together and discuss, operationalize, and refine each code. We will then generate “second-level codes” which consider categories or deeper meanings among first-level codes. During this process we will examine interrelationships and networks among codes and build a preliminary thematic framework. Transcripts will then be recoded and codes refined through further discussion and consensus, as needed. Participant and group “fit” with the framework will also be assessed, with confirmatory and disconfirmatory evidence for the model examined. Participant matrices may also be utilized to examine variance in themes across participants and key demographic factors, pre-post intervention change, or usage patterns. Interviews will be coded using qualitative content analysis.

Quantitative Data Analyses: Quantitative analyses will be largely descriptive, as appropriate for pilot trials (Lancaster et al., 2004) and will include effect sizes and 95% confidence intervals of the following measures in the assessment battery:

- FASD Knowledge survey
- Attributions and Behavioral Strategies
- Perceived Self-Efficacy (TSES)
- Study Design Feasibility and Acceptability (SES)
- Program Satisfaction (uMARS)

The below table summarizes how each analysis will address each sub-aim of the current study.

Aim	Evaluated Using
Intervention Feasibility	
• technological functionality	uMARS means/standard deviations; website crash reports; user experience interviews

• acceptability of website	uMARS means/standard deviations; user experience interviews
• typical usage patterns	Website usage data, including frequency, length, and timing of use
Study Design Acceptability	
• enrollment and attrition rates	N consented; N with complete data; rate of attrition
• acceptability of randomization and control condition	SES means/standard deviations; user experience interviews

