• assessment acceptability and sensitivity	Rate of assessment completion; pre-post effect sizes and 95% confidence intervals
• optimal intervention length	Website usage patterns
• predictors of attrition	Rate of attrition; demographic and baseline variables

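### The attributions measure (RCB) is not given at baseline, so no pre-post effect size for attributions can be computed in the immediate-access group

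*Combined protocol and SAP*

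**What the plan says.** Section 9 (Study Assessment Battery) describes the RCB as measuring attributions "across seven subscales of behavior and willful or ability-based attributions". It has 30 items and is marked at T2 and T3, with the baseline cell empty. FASD knowledge, the TSES, Behavioral Strategies and time spent on the student are marked at all three timepoints. The row "Total number of items at each timepoint" gives 116 at baseline, 149 (Group 1) and 117 (Group 2) at T2, and 139 at T3.

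On timing, Section 9 states: "Once baseline surveys are complete, subjects in Group 1 will receive immediate access to the website". Group 2 gets access after its T2 assessment.

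Section 17 lists "Attributions and Behavioral Strategies" among the measures to be reported with effect sizes and 95% confidence intervals. The row of its aims table on assessment acceptability and sensitivity reads "Rate of assessment completion; pre-post effect sizes and 95% confidence intervals". That row names no measure, group or pair of timepoints.

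Two other places show why attributions are measured. Section 2 says that educating teachers "is hypothesized to help them to modify their attributions" of the student's behavior. The website description in Section 9 says the study will "measure its preliminary effect on these outcomes in teachers", following a list of caregiver outcomes that includes attributions.

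No section explains why the RCB is left out at baseline.

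**The concern.** A pre-post effect size needs a score before exposure and one after. Group 1 has no attribution score before exposure, because its first RCB comes after six weeks with the website. Three things follow for attributions:

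- Group 1 has no pre-post estimate.
- Neither group has a change score over the randomised period (baseline to T2), so Group 2 has no control-period change.
- The T2 comparison between groups cannot be adjusted for baseline RCB.

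Attribution change is a link in the mechanism set out in Section 2, and the pilot is meant to inform a later RCT. Whether the RCB responds to the website bears on the choice of measures for that trial. Behavioral Strategies, which was normed together with the RCB and shares its bullet in Section 17, does have a baseline. That makes the gap look like an oversight, though the documents do not settle this.

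**Working it through.** **Is the empty cell real?** The item counts in the Section 9 table were added over the measures marked at each timepoint.

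- Baseline: 39 (screening and demographics) + 28 (knowledge) + 10 (TSES) + 36 (strategies) + 3 (time) = 116. Printed: 116. With the RCB it would be 116 + 30 = 146.
- T2, Group 2: 28 + 10 + 30 (RCB) + 36 + 3 + 10 (SES) = 117. Printed: 117.
- T2, Group 1: 117 + 32 (uMARS) = 149. Printed: 149.
- T3: 28 + 10 + 30 + 36 + 3 + 32 = 139. Printed: 139.

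All four totals reproduce. The baseline total does so only without the RCB, and the others only with it. The blank is not an artefact of text extraction.

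**Which RCB scores precede access?**

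| | Baseline | T2 | T3 | Pre-post pair |
|---|---|---|---|---|
| Group 1 | none | after access | after access | none |
| Group 2 | none | before access | after access | T2 to T3 |

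The Group 1 change from T2 to T3 reflects continued access, not before versus after.

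**Size.** Section 5 plans 90 enrolled with 45% attrition: 90 × 0.55 = 49.5, or about 25 completers per group. The plan gives no correlation r between two RCB administrations, so r = 0.3, 0.5 and 0.7 are assumed. SDs are taken as equal, and results are in SD units.

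- Lost Group 1 pre-post estimate, 95% CI half-width = t(24) × √(2(1 − r)/25), with t(24) = 2.064:
  - r = 0.3: 2.064 × 0.237 = 0.49
  - r = 0.5: 2.064 × 0.200 = 0.41
  - r = 0.7: 2.064 × 0.155 = 0.32
- Remaining unadjusted T2 contrast, half-width = t(48) × √(2/25) = 2.011 × 0.283 = 0.57.
- If a baseline-adjusted T2 analysis were used (the plan specifies none), lacking baseline RCB would widen its CI by 1/√(1 − r²) − 1, which is 4.8%, 15.5% and 40.0% at the three values of r. This assumes that no other baseline covariate is related to the T2 score.

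Both the T2 contrast and a baseline-to-T2 change need data only up to T2, so more than 25 per group could contribute. At the ceiling of 45 per group (90/2, no loss before T2), the unadjusted T2 half-width is t(88) × √(2/45) = 1.987 × 0.211 = 0.42.

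**The case against.** The strongest reply is that no stated analysis is strictly blocked. The sensitivity row names no group, so the Group 2 change from T2 to T3 satisfies it literally, and the randomised T2 contrast supplies an attribution effect size with its interval. The Section 17 list also includes the SES and uMARS, which can have no pre-access value, so being listed there does not by itself promise a baseline-to-T2 estimate. Neither hypothesis in Section 1 mentions attributions, and the analysis is mainly descriptive.

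Much of this stands, and it limits the weight of the point. The T2 contrast is a valid randomised comparison and informs sensitivity. The half-widths above belong to different estimands, an uncontrolled change and a between-group difference, so the narrower one is not simply better information about effect. The widening figures are upper bounds if other baseline measures, such as Behavioral Strategies, predict the T2 RCB.

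It does not remove the gap. The SES and uMARS ask about the study and the website, so a missing baseline is inherent to them. The RCB could be asked at baseline, as the other teacher outcomes are. The Group 2 change uses only about half of the planned completers and has no unexposed concurrent comparator, because Group 1 already has access.

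Limiting burden would be a defensible reason for the omission, but the plan does not give it.

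**Conclusion.** The concern holds. The schedule provides no attribution score before access in Group 1, so the pre-post effect size that Section 17 uses to judge sensitivity cannot be computed there for a measure that Section 17 lists. The loss covers all of Group 1, about 25 of 50 planned completers, and extends to the control-period change and to baseline adjustment of the T2 contrast.

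That the score is missing rests only on the schedule and its printed totals. The precision figures are illustrative and depend on the assumed r, equal SDs and 25 per group.

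The consequence is modest: one measure within one of the eight sub-aims. Enrollment, attrition, usage and acceptability are not affected. It is still worth correcting, because the remedy is cheap and the data cannot be recovered for a participant once Group 1 access begins.

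**What to change.** Mark the RCB at baseline in the Section 9 battery and change the baseline total from 116 to 146. This gives a Group 1 pre-post estimate, a control-period change in Group 2 and the option of baseline adjustment at T2.

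If the omission is deliberate, say so in Section 17. State there that attributions have no Group 1 pre-post estimate and will be reported as the T2 between-group contrast plus the Group 2 change from T2 to T3. The same statement is needed for any participants already past baseline.

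The first option costs a protocol and IRB amendment and 30 more baseline items: 30/116 = 26% more overall. Section 9 says "After randomization, subjects will complete the remaining baseline surveys", so the added items would fall after randomisation. If all 39 screening and demographic items come before it, the post-randomisation load rises from 116 − 39 = 77 to 107 items (30/77 = 39%). In a trial that assumes 45% attrition, some added early loss is possible. A 146-item baseline stays below the 149 items Group 1 answers at T2, but it would become the longest session for Group 2 (117 at T2, 139 at T3). The fallback costs only the added statement in Section 17.

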## 10. AUDIO/VIDEO RECORDINGS

Qualitative interviews will be recorded using HIPAA-compliant Zoom. Research staff will be at Mt. Hope Family Center when completing interviews, using UR computers. Recordings will be uploaded from the local machine as soon as possible to a URMC Box folder for this project managed by the IT team at Mt. Hope Family Center. Only research staff involved on this project will have access to recordings. Recordings will then be transcribed verbatim by research staff. After all transcripts have been rechecked, audio and video recordings will be deleted.

## 11. RISKS TO SUBJECTS

Participants may experience psychological risks associated with participation in this study, such as discomfort or boredom in answering questions or providing feedback about the website. There is also a risk of loss of confidentiality. All data collected for the proposed

research study will be kept confidential to the extent allowed by law. Although it is unlikely given the nature of this study, if participants disclose that someone is being maltreated or is a danger to self or others, research staff will need to break confidentiality to make a report to the appropriate authority to ensure safety, as mandated by law. We believe that all identified risks are reasonable given the proposed procedures for protecting against risk.

### **Protections Against Risks**

To minimize risk associated with psychological discomfort, participants will be given the option to skip questions they feel uncomfortable answering. Multiple procedures will be implemented to protect participant confidentiality. In terms of data storage and management, any hard copy data will be secured in locked file cabinets within locked offices, available only to program staff. Electronic data will be stored on URMC managed Box folder for this project, and only project staff with appropriate permissions will be able to access the data. Forms with identifying information will be separated from the data collected and only subject numbers will be retained in data analysis files.

Multiple levels of protection will be put in place to reduce the risk of loss of confidentiality for data collected through the website. Collected data will be stored using a random code that will not allow direct identification of a particular subject, while any data that identify the user will be stored separately. All the connections with the website, as well as connections between the website and the database, will use state of the art authentication and encryption algorithms (e.g., HTTPS, SSL and TLS). The Cloud architecture and services will be built and are managed by [name], under a University-managed Azure account, and in compliance with University policy. Security and Benchmark compliance reports will be received and reviewed by [name]. Access to the data stored on the Cloud will be restricted, access to the data will be logged and backups will be created to allow the users to restore them if/when necessary. Appropriate policies will be set up so that users will be able to add and modify their own data but will be prevented from viewing and modifying other users' data. Unique login credentials will be provided to each participant and will be required to access the content of FMF Connect Teachers companion website. No personal data will be stored by the website on the participant's device.

All information obtained for research will be kept strictly confidential (as allowed by law) by research staff. Participants will be told about all exceptions (e.g., child/dependent adult abuse, harm to self or others) to confidentiality during the consent process. Project staff will be closely supervised by [name] and instructed on confidentiality, including what information is confidential, the limits of confidentiality, and to whom to report concerns.

The FMF Connect Teacher Companion website is viewed as a “value-added” intervention. Participants can continue to seek information on FASD elsewhere or use their preferred behavior management strategies. The alternative to participating in this study is not to participate.

## **12. POTENTIAL BENEFITS TO SUBJECTS**

Participants may not experience any direct benefits from participating in this study. However, participants in prior FASD research studies at MHFC have commented on how they value and derive personal satisfaction in participating in research to increase knowledge

about this under-recognized condition and effective strategies to benefit other people with FASD. It is also possible, although not guaranteed, that subjects might derive benefit from using the FMF Connect Teacher Companion website. Possible benefits may include improved self-efficacy, increased knowledge about FASD, and improved classroom management and teaching.

### **13. COSTS FOR PARTICIPATION**

There are no costs to participate.

### **14. PAYMENT FOR PARTICIPATION**

Subjects will receive \$25 upon completion of assessments at each timepoint. Those who are selected for and complete an interview will receive an additional \$25. Payments will be gift cards. If a participant withdraws from the study they will receive payment for the timepoints they did complete but not for any future timepoints.

